18.3 CTCAE Toxicities of Laboratory Evaluations

Laboratory Evaluation	Toxicity	Grade	Value
Albumin	LOW	1	<LLN - 30 g/L
	LOW	2	<30 - 20 g/L
	LOW	3	<20 g/L
Alkaline Phosphatase	HIGH	1	>1.0 - 2.5 x ULN
	HIGH	2	>2.5 - 5.0 x ULN
	HIGH	3	>5.0 - 20.0 x ULN
	HIGH	4	>20.0 x ULN
Alanine Aminotransferase	HIGH	1	>1 - 3.0 x ULN
	HIGH	2	>3 - 5.0 x ULN
	HIGH	3	>5 - 20.0 x ULN
	HIGH	4	>20 x ULN
Aspartate Aminotransferase	HIGH	1	>1 - 3.0 x ULN
	HIGH	2	>3 - 5.0 x ULN
	HIGH	3	>5 - 20.0 x ULN
	HIGH	4	>20 IU/L
Calcium	HIGH	1	> ULN - 2.9 mmol/L;
	HIGH	2	>2.9 - 3.1 mmol/L;
	HIGH	3	>3.1 - 3.4 mmol/L
	HIGH	4	>3.4 mmol/L
	LOW	1	< LLN - 2.0 mmol/L
	LOW	2	<2.00 - 1.75 mmol/L
	LOW	3	<1.75 - 1.5 mmol/L
	LOW	4	<1.50 mmol/L
Cholesterol	HIGH	1	>ULN - 7.75 mmol/L
	HIGH	2	>7.75 - 10.34 mmol/L
	HIGH	3	>10.34 - 12.92 mmol/L
	HIGH	4	>12.92 mmol/L
Creatine Kinase	HIGH	1	>1.0 - 2.5 x ULN
	HIGH	2	>2.5 - 5 x ULN
	HIGH	3	>5.0 - 10 x ULN
	HIGH	4	>10.0 x ULN
Creatinine	HIGH	1	>1.0 - 1.5 x ULN
	HIGH	2	>1.5 - 3.0 x ULN
	HIGH	3	>3.0 - 6.0 x ULN
	HIGH	4	>6.0 x ULN
Gamma Glutamyl Transferase	HIGH	1	>1.0 - 2.5 x ULN
	HIGH	2	>2.5 - 5.0 x ULN
	HIGH	3	>5.0 - 20.0 x ULN
	HIGH	4	>20.0 x ULN
Glucose	HIGH	1	>ULN - 8.9 mmol/L
	HIGH	2	>8.9 - 13.9 mmol/L
	HIGH	3	>13.9 - 27.8 mmol/L
	HIGH	4	>27.8 mmol/L
	LOW	1	< LLN - 3.0 mmol/L
	LOW	2	<3.0 - 2.2 mmol/L
	LOW	3	<2.2 - 1.7 mmol/L
LOW	4	<1.7 mmol/L	

Laboratory Evaluation	Toxicity	Grade	Value
Hemoglobin	HIGH	1	> ULN - ULN + 20 g/L
	HIGH	2	> ULN + 20 - ULN + 40 g/L
	HIGH	3	> ULN + 40 g/L
	LOW	1	< LLN - 100 g/L
	LOW	2	<100.0 - 80 g/L
	LOW	3	<80.0 g/L
Lipase	HIGH	1	>1.0 - 1.5 x ULN
	HIGH	2	>1.5 - 2.0 x ULN
	HIGH	3	>2.0 - 5.0 x ULN
	HIGH	4	>5.0 x ULN
Lymphocytes	HIGH	2	>4.00 - 20.00 10 ⁹ /L
	HIGH	3	>20.00 10 ⁹ /L
	LOW	1	< LLN - 0.8 10 ⁹ /L
	LOW	2	<0.80 - 0.5 10 ⁹ /L
	LOW	3	<0.50 - 0.2 10 ⁹ /L
Magnesium	LOW	4	<0.20 10 ⁹ /L
	HIGH	1	>ULN - 1.23 mmol/L
	HIGH	3	>1.23 - 3.30 mmol/L
	HIGH	4	>3.30 mmol/L
	LOW	1	< LLN - 0.5 mmol/L
	LOW	2	<0.50 - 0.4 mmol/L
	LOW	3	<0.40 - 0.3 mmol/L
Neutrophils	LOW	4	<0.30 mmol/L
	LOW	1	< LLN - 1.5 10 ⁹ /L
	LOW	2	<1.50 - 1.0 10 ⁹ /L
	LOW	3	<1.00 - 0.5 10 ⁹ /L
Phosphate; Phosphorus	LOW	4	<0.50 10 ⁹ /L
	LOW	1	< LLN - 0.8 mmol/L
	LOW	2	<0.80 - 0.6 mmol/L
	LOW	3	<0.60 - 0.3 mmol/L
Platelets	LOW	4	<0.30 mmol/L
	LOW	1	< LLN - 75.0 10 ⁹ /L
	LOW	2	<75 - 50.0 10 ⁹ /L
	LOW	3	<50 - 25.0 10 ⁹ /L
Potassium	LOW	4	<25 10 ⁹ /L
	HIGH	1	>ULN - 5.5 mmol/L
	HIGH	2	>5.5 - 6.0 mmol/L
	HIGH	3	>6.0 - 7.0 mmol/L
	HIGH	4	>7.0 mmol/L
	LOW	2	< LLN - 3.0 mmol/L
	LOW	3	<3.0 - 2.5 mmol/L
Amylase	LOW	4	<2.5 mmol/L
	HIGH	1	>1.0 - 1.5 x ULN
	HIGH	2	>1.5 - 2.0 x ULN
	HIGH	3	>2.0 - 5.0 x ULN
Sodium	HIGH	4	>5.0 x ULN
	HIGH	1	> ULN - 150 mmol/L
	HIGH	2	>150 - 155 mmol/L
	HIGH	3	>155 - 160 mmol/L

Laboratory Evaluation	Toxicity	Grade	Value
	HIGH	4	>160 mmol/L
	LOW	1	< LLN - 130 mmol/L
	LOW	3	<130 - 120 mmol/L
	LOW	4	<120 mmol/L
Total Bilirubin	HIGH	1	>1.0 - 1.5 x ULN
	HIGH	2	>1.5 - 3.0 x ULN
	HIGH	3	>3.0 - 10.0 x ULN
	HIGH	4	>10.0 x ULN
Triglycerides	HIGH	1	>1.71 - 3.42 mmol/L
	HIGH	2	>3.42 - 5.7 mmol/L
	HIGH	3	>5.70 - 11.4 mmol/L
	HIGH	4	>11.40 mmol/L
White Blood Cell	HIGH	3	>100.0 10 ⁹ /L
	LOW	1	< LLN - 3.0 10 ⁹ /L
	LOW	2	<3.0 - 2.0 10 ⁹ /L
	LOW	3	<2.0 - 1.0 10 ⁹ /L
Uric Acid	HIGH	3	> ULN - 0.59 mmol/L
	HIGH	4	>0.59 mmol/L

LLN= lower limit of normal; ULN= upper limit of normal

ELECTRONIC SIGNATURES

Document: ctp-ms100070-0035-iap-v2-0

Signed By	Event Name	Meaning of Signature	Server Date (dd-MMM-yyyy HH:mm 'GMT'Z)
PPD	Task Completed (Approval eSign): Approved	Technical Approval	16-Aug-2019 02:18

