## **7.4.1 Adverse Events**

### **7.4.1.1 Adverse Event Definitions**

#### **Adverse Event**

An AE is any untoward medical occurrence in a subject or clinical investigation subject administered a pharmaceutical product, which does not necessarily have a causal relationship with this treatment. An AE can therefore be any unfavorable and unintended sign (including an abnormal laboratory finding), symptom, or disease temporally associated with the use of a medicinal product, whether or not considered related to the medicinal product.

In cases of surgical or diagnostic procedures, the condition/illness leading to such a procedure is considered as the AE rather than the procedure itself.

The Investigator is required to grade the severity/intensity of each AE.

Investigators will reference the NCI-CTCAE v4.03 (publication date: 14 June 2010). This is a descriptive terminology that can be used for AE reporting.

A general grading (severity/intensity) scale is provided at the beginning of the referenced document, and specific event grades are also provided.

If the severity/intensity of a particular AE is not specifically graded by the guidance document, the Investigator is to revert to the general definitions of Grade 1 through Grade 5 and use his or her best medical judgment.

The 5 general grades are:

- Grade 1: Mild
- Grade 2: Moderate
- Grade 3: Severe
- Grade 4: Life-threatening or disabling
- Grade 5: Death.

According to the Sponsor's convention, if a severity/intensity of Grade 4 or Grade 5 is applied to an AE, then the Investigator must also report the event as an SAE. However, a laboratory abnormality with a severity/intensity of Grade 4, such as anemia or neutropenia, is considered serious only if the condition meets one of the serious criteria described below.

In the case of death, the primary cause of death (the event leading to death) should be recorded and reported as an SAE. "Fatal" will be recorded as the outcome of this respective event; death will not be recorded as separate event. Only if no cause of death can be reported (eg, sudden death, unexplained death), the death per se might be reported as an SAE.

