15.3 Clinical Laboratory Evaluation

All laboratory assessments are performed at local laboratories and comply with local requirements.

Laboratory values (including corresponding normal ranges) from local laboratories will be converted into the standard units by data management. The results in standard units will be used for the analyses.

Laboratory results will be classified according to the NCI-CTCAE toxicity grading version 4.03. If toxicities for high and low values of a specific parameter are defined, these toxicities will be analyzed separately for the parameter as “Parameter low” and “Parameter high” (appendix 18.3).

Laboratory results that are not part of the NCI-CTCAE will be presented according to the categories: below normal limits, within normal limits and above normal limits (according to the local laboratories normal ranges).

- **Hematology:** Hematocrit, Hemoglobin, Platelet count, Red blood cells (RBC) count, White Blood Cell Count, Absolute lymphocytes count, Lymphocytes, Absolute Neutrophils count, Neutrophils, Absolute monocyte count, Monocytes, Absolute eosinophil count, Eosinophils, Absolute basophil count, Basophils, RBC morphology, Absolute reticulocytes count, Reticulocytes, Mean corpuscular hemoglobin (MCH), Mean corpuscular volume (MCV), Mean corpuscular hemoglobin concentration (MCHC).
- **Hemostaseology:** Activated partial thromboplastin time (aPTT), Prothrombin time (PT), International Normalized Ratio (INR).
- **Biochemistry:** Albumin, Alkaline phosphatase, Alanine Aminotransferase (ALT), Amylase, Aspartate Aminotransferase (AST), Gamma Glutamyl Transpeptidase (GGT), Blood Urea Nitrogen (BUN), Urea, Calcium, Chloride, Cholesterol, Creatine kinase, Creatinine, C-Reactive Protein (CRP), Glucose, Lactate dehydrogenase (LDH), Lipase, Phosphorus, Magnesium, Potassium, Sodium, Total bilirubin, Protein total, Uric acid, Triglycerides, Hemoglobin A1c.
- **Hormonal tests:** Free Thyroxine (T4), Thyroid-Stimulating Hormone (TSH), Follicle-stimulating hormone.
- **Urinalysis:** pH, Specific gravity, Protein content, Sediment analysis, Albumin, Immunoglobulin G.

NCI-CTCAE grades available:

The laboratory toxicities will be tabulated by the worst on-treatment CTCAE grade or the shift of CTCAE grade from baseline to worst grade during on-treatment period using descriptive statistics (count and percentage). The highest CTCAE grade during the on-treatment period is considered as the worst grade for the summary.

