- The worst grade during the on-treatment period will be summarized considering only patients with post baseline laboratory samples: Laboratory tests by NCI-CTCAE grade (0, 1, 2, 3, 4, and missing).

The shift table will summarize baseline CTCAE grade vs. the worst on-treatment CTCAE grade (grade = 0, 1, 2, 3, 4, missing). The above analyses apply to the following hematology and biochemistry parameters which can be graded per NCI-CTCAE:

- Hematology: Hemoglobin, Lymphocytes, Neutrophils, Platelets, White Blood Cell.

- Biochemistry: Creatinine, Alanine Aminotransferase, Aspartate Aminotransferase, Gamma Glutamyl Transferase, Total Bilirubin, Lipase, Amylase, Albumin, Alkaline Phosphatase, Glucose, Uric Acid, Sodium, Potassium, Calcium, Magnesium, Cholesterol, Creatine kinase, Triglyceride, Phosphorus.

Tables will summarize, separately for hematology and biochemistry parameters, the shift from baseline grade to worst on-treatment grade by parameters and dose level.

NCI-CTCAE grades not available:

The worst on-treatment value for hematology and biochemistry parameters which cannot be graded per NCI-CTCAE will be summarized by parameter according to the local laboratories normal ranges as follows:

- Shift from baseline value (low, normal, high) to above normal during on-treatment period
- Shift from baseline value (low, normal, high) to below normal during on-treatment period.

The above analyses apply to the following hematology and biochemistry parameters which cannot be graded per NCI-CTCAE:

- Hematology: Hematocrit, Red Blood Cells, RBC morphology, Monocytes, Eosinophils, Basophils, Reticulocytes, MCH, MCV, MCHC.
- Biochemistry: Total Protein, Blood Urea Nitrogen, Blood Urea, Chloride, C-Reactive Protein (CRP), Glucose, Lactate dehydrogenase, Hemoglobin A1c.

Quantitative data will also be examined for trends using descriptive statistics (n, missing, mean, SD, median, Q1, Q3, minimum, and maximum) of actual values, absolute changes and percent changes from baseline to each visit over time. This summarization will apply to hematology and chemistry parameters with numeric results assessed at baseline, post-baseline, discontinuation, end of treatment, and safety follow-up visits.

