Listing of clinically significant hematology values and listing of clinically significant biochemistry values will also be provided. Clinically significant values are defined as values with associated NCI-CTCAE grade greater or equal to 3. The following information will be included in those listings:

- Selected dosing information: date of first/last administration
- Laboratory parameter with unit
- Visit of laboratory parameter measurement
- Collection date of laboratory parameter
- Value of laboratory parameter
- Local laboratories normal ranges for laboratory parameter (lower limit of normal and upper limit of normal)

- Normal range indicator for value of the laboratory parameter (Low, Normal, High)
- Associated grade for value of the laboratory parameter according to NCI-CTCAE if applicable.

Other laboratory parameters

The following laboratory parameters collected in the CRF will be presented in specific listing presenting all collected data-fields in the CRF.

- Hemostaseology: Activated partial thromboplastin time (aPTT), Prothrombin time (PT), International Normalized Ratio (INR)
- Hormone: Free T4 and TSH
- Urinalysis: all urinalysis parameters
- Pregnancy test
- Serology

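### SAP Appendix 18.3 makes any uric acid value just above the upper limit of normal a Grade 3 on value alone, so trivial elevations enter the Grade 3 laboratory tables and the clinically significant listing

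*SAP*

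**What the plan says.** SAP Section 15.3 sets the grading basis: "Laboratory results will be classified according to the NCI-CTCAE toxicity grading version 4.03". Appendix 18.3 turns this into numeric cut-offs and carries no qualifier for symptoms or consequences.

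- **Uric acid.** The band "> ULN - 0.59 mmol/L" is HIGH Grade 3. Values above 0.59 mmol/L are HIGH Grade 4. No lower grade is given.
- **Potassium, low side.** The band "< LLN - 3.0 mmol/L" is Grade 2 and "<3.0 - 2.5 mmol/L" is Grade 3. No Grade 1 is given.

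Both analytes are on the Section 15.3 list of gradable biochemistry parameters ("Glucose, Uric Acid, Sodium, Potassium, Calcium, Magnesium"). The highest on-treatment grade goes into the summary, and "The shift table will summarize baseline CTCAE grade vs. the worst on-treatment CTCAE grade". A separate listing follows this rule: "Clinically significant values are defined as values with associated NCI-CTCAE grade greater or equal to 3".

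For scale, the general grading in Protocol Section 7.4.1.1 reads "Grade 3: Severe".

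**The concern.** A uric acid result at ULN is Grade 0, and the next reportable value above it is Grade 3. A subject who drifts marginally out of range would show a shift from 0 to 3. A subject who enters the study marginally out of range would show Grade 3 at baseline, and uric acid is not among the eligibility limits in Protocol Section 5.3.1, so this can happen. Either subject would appear in the listing meant for values that matter clinically.

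Laboratory safety is reported by dose level in cohorts of 3 to 6. A single misgraded subject is therefore visible in the Grade 3 column and could be read as a signal at that dose.

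**Working it through.** **Step 1: apply the appendix literally.** The documents do not give local normal limits, so the limits below are assumptions. The grade is the same across the range.

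| Analyte | Assumed limit (mmol/L) | Value tested | Grade | In the Grade 3 or higher listing? |
|---|---|---|---|---|
| Uric acid | ULN 0.36, 0.42, 0.48 | at ULN | 0 | no |
| Uric acid | ULN 0.36, 0.42, 0.48 | ULN + 0.001 | 3 | yes |
| Potassium | LLN 3.4, 3.5, 3.6 | at LLN | 0 | no |
| Potassium | LLN 3.4, 3.5, 3.6 | LLN − 0.01 | 2 | no |

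Low potassium enters the listing only below 3.0 mmol/L.

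**Step 2: compare with the rest of Appendix 18.3.** Count the scales whose first band starts at a normal limit.

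- HIGH scales starting at ULN: alkaline phosphatase, ALT, AST, calcium, cholesterol, creatine kinase, creatinine, GGT, glucose, hemoglobin, lipase, magnesium, potassium, amylase, sodium and total bilirubin. These 16 all begin at Grade 1. Uric acid, the seventeenth, begins at Grade 3.
- LOW scales starting at the lower limit of normal (LLN): albumin, calcium, glucose, hemoglobin, lymphocytes, magnesium, neutrophils, phosphate, platelets, sodium and white cells. These 11 all begin at Grade 1. Potassium, the twelfth, begins at Grade 2.
- Together: 16 + 11 = 27 of 17 + 12 = 29 begin at Grade 1.

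**Step 3: exposure to the error.** Protocol Table 7-1 puts uric acid in the full chemistry panel only. Table 1-1 schedules that panel at screening, Days 43 and 85, then every 6 weeks, and at end of treatment. Each on-treatment draw can set a subject's worst grade.

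**Step 4: weight of one subject.** 1/6 = 16.7% and 1/3 = 33.3%, that is 17 to 33 percentage points of a cohort. Section 15.3 restricts the worst-grade table to subjects with post-baseline samples, so the actual denominator may be smaller and the share larger.

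**Step 5: how many subjects?** The documents do not say how often uric acid will be raised. As an illustration only, assume ULN is a 97.5th percentile and take three on-treatment draws in otherwise normal subjects. With fully correlated draws, 2.5% have at least one raised value. With independent draws, 1 − 0.975³ = 7.3%. For 21 subjects that is 21 × 0.025 = 0.5 to 21 × 0.073 = 1.5.

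**The case against.** **Skipped grades are not unusual in this table.** Lymphocytes HIGH starts at Grade 2, magnesium HIGH and sodium LOW go from 1 to 3, and white cells HIGH has only Grade 3. A missing grade is therefore not proof of error. This stands as a caution, but none of these examples puts a value just outside the normal limit at Grade 3.

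**The governing standard is CTCAE v4.03, whose text is not in the documents.** This stands. The evidence here is internal, and any replacement grade needs checking against the source.

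**A row may be missing.** In the copy of the appendix read here, some labels are displaced (the lowest potassium row stands beside amylase), and no Grade 4 row for low white cells appears just above uric acid. A lost row cannot be fully excluded, but it would not help. The Grade 3 band itself starts at ULN, so a lost Grade 1 or 2 row would overlap it, and taking the highest grade would still give 3.

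**The outputs partly protect the reader.** The listing shows the value, the local limits and a range indicator, and Section 15.3 also summarises actual values and changes by visit. The general severity labels belong to adverse events, while the laboratory tables show numbers only. This lessens the harm in the listing. It does not correct the counts in the worst-grade and shift tables.

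**Stronger readings that the documents do not support:**

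- A reader might infer that false dose-limiting toxicities follow. SAP Section 15.1 takes them from the adverse event form, and Protocol Section 7.4.1.1 requires confirmation by the Safety Monitoring Committee.
- A reader might infer that trivial low potassium is also reported as Grade 3. It is Grade 2 and is not listed.
- A reader might blame the grade label for hiding worsening between ULN and 0.59 mmol/L. That follows from the width of the band and would remain under a Grade 1 label.

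**Conclusion.** The point holds for uric acid. Followed exactly, the SAP assigns Grade 3 to every value from just above ULN to 0.59 mmol/L. Those subjects appear in the Grade 3 column, can show false shifts from 0 to 3 or a Grade 3 baseline, and enter the clinically significant listing.

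Each affected subject is 17 to 33 percentage points of a cohort of 6 or 3. The number affected is unknown; 0.5 to 1.5 of 21 rests wholly on the assumptions in Step 5 and should not be quoted as an estimate. The conclusion about the grade rests on no assumption beyond the appendix being programmed as printed.

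Laboratory parameters are additional to the secondary endpoints (Protocol Sections 8.3.2 and 8.3.3). The primary endpoint and dose escalation are unaffected. For low potassium the effect is smaller: mild values show as Grade 2 where the other 11 LLN-starting scales show Grade 1.

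**What to change.** 1. In Appendix 18.3, change the uric acid row from ULN to 0.59 mmol/L from Grade 3 to Grade 1 for value-only grading.
2. State that any higher grade that depends on symptoms or consequences is taken from the adverse event page, where the investigator already grades severity.
3. Before programming, check both uric acid rows against CTCAE v4.03. This includes the row above 0.59 mmol/L, which would otherwise stay Grade 4 on value alone and leave a scale running from 1 straight to 4.
4. Check the low potassium row from LLN to 3.0 mmol/L in the same way and correct it if needed.

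The cost is a few cells in one SAP appendix and the matching grading code. No new data are needed.
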